sham or active rTMS for reducing pain or depression but active rTMS was associated with a significant improvement on quality of life (11). Saltychev et al. revealed moderate evidence that rTMS is not more effective than sham in reducing the severity of pain in FMS (20). Hou et al. suggested that M1 stimulation may be better in pain reduction and the DLPFC may be better in depression improvement (10). On contrary to this study, recently Lefaucheur et al. reported that high frequency-rTMS of the left DLPFC is more efficacious on pain, while high frequency -rTMS of the left M1 is more efficacious on the quality of life (21). In addition, there are very few studies investigating the effect of TMS treatment on cognitive dysfunction, which is an important problem in FMS (22). It is clear that there is still a need for further studies on the exact clinical effects of rTMS treatment in FMS.

Therefore, this study aimed to evaluate the effectiveness of 10 Hz neuronavigated rTMS to the left DLPFC on pain, stiffness, fatigue, depression/anxiety, quality of life and cognitive functions in FMS.

Methods

Participants

Participants were recruited from Physical Medicine and Rehabilitation (PMR) outpatient clinics of a university hospital. Twenty patients (mean ages: 45.25 ± 9.08 years, range 29 to 64 years; 20 females) with FMS who met the following inclusion criteria were included in the study: (1) adults (age between 18-65 years); (2) diagnosis of FMS according to 2016 Fibromyalgia diagnostic criteria; (3) the mean pain intensity is VAS $\geq 4 / 10$; (4) stable treatment for at least last 3 months. Patients were excluded: if they had a clinical condition to be contraindicated for TMS (e.g. metallic implant, cardiac pace, pregnancy, lactation, epilepsy, head trauma, history of cranial operation); significant medical or psychiatric illness including malignancy, major depression, personality disorder, history of substance or alcohol abuse; major orthopedic/ neurological problems that limit daily life activities; pregnancy/breastfeeding; concomitant inflammatory rheumatic diseases, autoimmune diseases or other painful disorders and patients who have received TMS treatment before.

Study design and ethics

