This is a single-center, prospective, randomized, double-blind, sham-controlled study in two-arm parallel-group design. Participants were informed about the study and provided written informed consents. The protocol was performed in accordance with the ethical standards laid down in the 1964 Declaration of Helsinki and approved by the local Research Ethics Committee (Approval number: 14.03.2019/25). This study was registered on www.clinicaltrials.gov with ID NCT03909009.

Demographics

At baseline, demographic information including age, gender, weight, height, body mass index (BMI), dominant side, marital status, education level, occupation, disease duration, additional diseases, smoking and alcohol use, drugs used for FMS treatment were questioned.

Randomization and blinding

Randomization was performed using computer-generated block randomization with 1:1 allocation between the active rTMS group (Group A) and the sham-control group (Group B) by an independent researcher not involved in the rTMS treatment sessions, patient selection or clinical evaluations. Two different researchers conducted other parts of this double-blind study. One of the researchers performed patient selection and interventions. The second researcher was blinded about the distribution of groups, patient selection and interventions. The blind investigator performed patient evaluations at the beginning of treatment, at the end of the 2nd and 6th weeks. The patients did not know which group they were in during the study.

Outcome assessment and data collection

After recording general demographic data clinical assessments were performed. All clinical outcome measures were assessed by an experienced researcher who was familiarized with the scales and tests used in this study and who was blinded of the group assignment. The clinical assessments consisted of six main sections: (1) Pain severity (VAS-pain) (2) Stiffness severity (VAS-stiffness) (3) Fibromyalgia Impact Questionnaire (FIQ) (4) Fatigue Severity Scale (FSS) (5) Hospital Depression Anxiety Scale (HADS) (6) Addenbrook Cognitive Examination - revised version (ACE-R)

Primary clinical outcome measure included VAS-pain (at the end of the 2nd week) whereas secondary outcome measures included FIQ and VAS-pain scores at the end of the 6th week.

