Visual analog scale: Pain severity and stiffness severity were evaluated with VAS. VAS is a psychometric measuring instrument designed to document the severity of disease-related symptoms. In this study, the severity of the pain and stiffness experienced at rest were assessed on a 10cm VAS (Total score: 0-10)(Higher scores mean a worse outcome) (0=no pain/stiffness, 10=severe pain/stiffness) at baseline, at 2nd week and at the end of treatment (6th week) (23).

Fibromyalgia Impact Questionnaire (FIQ): Functional health status and quality of life of the participants were assessed with the FIQ, which measures 10 different features (physical functioning, missed days of work, depression, anxiety, feeling good, morning tiredness, pain, stiffness, fatigue, and well-being over the past week). The total FIQ score is 0-80 points. High scores indicate low functionality level. In our study, FIQ was evaluated at baseline, at the end of the 2nd and 6th week (24).

Fatigue Severity Scale (FSS): Severity of fatigue was evaluated with FSS, a 9-item self-report questionnaire scale. Each item of this scale consists of statements that are scored on a seven-point Likert type scale ranging from 1 to 7. Total FSS score is calculated as mean value of the nine items. Higher scores indicate higher fatigue severity (Total score range: 1-7). FSS was assessed at baseline, at the end of the 2nd and 6th week (25).

Hospital Anxiety and Depression Scale (HADS): HADS is an assessment tool developed to identify the risk of anxiety and depression and measure its level and change of severity. Its subscales are anxiety and depression. It contains 14 questions in total, including 7 (odd numbers) measuring anxiety and 7 (even numbers) measuring

depression. The lowest and highest total score that a person can obtain from this scale are 0 and 42, respectively. High scores are associated with a worse psychiatric condition. HADS was evaluated at baseline and 6th week of study (26).

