Addenbrook Cognitive Examination Revised (ACE-R): Addenbrook Cognitive Examination-Revised is a brief cognitive test that consists of 5 basic sections: attention and orientation, memory, verbal fluency, language and visual-spatial abilities. Total score that can be obtained is 0-100. Higher scores are associated with a better cognitive state. ACE-R is considered useful in discriminating cognitively normal subjects from patients with mild cognitive impairment. ACE-R was assessed at baseline and 6th week of our study (27).

Interventions

Twenty patients were randomized into two groups. After randomization, group A received total 14 sessions of rTMS, 10 sessions daily (5 days/week, 2 weeks) and 4 sessions weekly (1 day/week, 4 weeks). Group B received sham treatment in the same sessions and time.

Neuronavigated repetitive transcranial magnetic stimulation: Brain images for participants were performed on a 1.5T magnetic resonance scanner (GE Sigma HDxt, General Electric Medical Systems, Milwaukee, WI, USA) using an eight-channel head coil. Magnetic resonance imaging (MRI) scans of each participant's brain were imported to the 3D guided neuronavigation device (NeNa-Neural navigator, The BrainTRAK™, Brain Science Tools BV, Utrecht, Netherlands). Then, we performed brain segmentation and the creation of stimulation target. The location of the left DLPFC was determined by an experienced researcher in accordance with the literature (28). These information were saved and used to target the left-DLPFC in the future sessions. The position of the TMS

coil and the patient's head was tracked using the BrainTRAKTM, a magnetic position tracking device built into the Neural Navigator.

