Database management and statistical analyses were performed by an independent researcher. The statistical analysis was performed by SPSS Statistics 22.0 (IBM Corp., Armonk, New York, ABD) software. As the descriptive statistics, the number of units (n), percent (%), mean \pm standard deviation ($\bar{x} \pm ss$), median [IQR (interquartile range)] values were given. Distributions of continuous variables were evaluated using the Shapiro-Wilk test and Q-Q plots. Pearson chi-square test, Fisher's Exact test, and independent samples t-test were performed to determine differences between the demographic and clinical characteristic of the groups. Wilcoxon's signed-rank test and Mann-Whitney U-test were used to determine differences within and between the groups' baseline, 2nd or 6th week outcome parameters. If the two groups met the assumptions in terms of pain, stiffness, FIQ, and FSS variables measured at three different times, they were compared using bidirectional (treatment method \times time) variance analysis in repeated measurements. The variables examined in the 95% confidence level and P values less than 0.05 were considered significant.

Ethics Committee Approval

Author declared that the research was conducted according to the principles of the World Medical Association Declaration of Helsinki “Ethical Principles for Medical Research Involving Human Subjects”, (amended in October 2013).

University local Research Ethics Committee Approval number: 14.03.2019/25

Informed Consent

Written informed consent was obtained from the patients who participated in this study

Declaration of conflicting interests

The authors declared no conflicts of interest with respect to the authorship and/or publication of this article.

Funding

This work was supported by Izmir Katip Çelebi University Scientific Research Project fund.

Acknowledgement

None

References

1. Clauw DJ. Fibromyalgia: a clinical review. *JAMA* 2014;311:1547-55.
3. Marques AP, Santo ASDE, Berssaneti AA, Matsutani LA, Yuan SLK. Prevalence of fibromyalgia: literature review update. *Rev Bras Reumatol Engl Ed* 2017;57:356-63.

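### No baseline adjustment or change score is stated for the between-arm comparison of HADS and ACE-R, which costs precision on mood and cognition but leaves the named outcomes untouched

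*Combined protocol and SAP*

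**What the plan says.** The Statistical analysis section names two kinds of outcome analysis.

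- Rank tests: "Wilcoxon's signed-rank test and Mann-Whitney U-test were used to determine differences within and between the groups' baseline, 2nd or 6th week outcome parameters".
- A two-way repeated-measures ANOVA with factors for arm and visit. It is both conditional and limited to listed variables: "If the two groups met the assumptions in terms of pain, stiffness, FIQ, and FSS variables measured at three different times".

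The outcome descriptions give HADS and ACE-R two visits each: "HADS was evaluated at baseline and 6th week of study" and "ACE-R was assessed at baseline and 6th week of our study". They are therefore outside the ANOVA both by name and by number of visits. The section names no covariate, change score or ANCOVA for any outcome.

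The aim at the end of Objectives covers "pain, stiffness, fatigue, depression/anxiety, quality of life and cognitive functions in FMS". The outcome hierarchy, under Outcome assessment and data collection, is narrower: "Primary clinical outcome measure included VAS-pain (at the end of the 2nd week) whereas secondary outcome measures included FIQ and VAS-pain scores" at week 6. HADS and ACE-R appear in neither tier.

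**The concern.** The treatment-by-time ANOVA is the only stated analysis that links follow-up to baseline and also compares the arms. For pain, stiffness, FIQ and FSS it is available if its assumptions hold. For mood and cognition it is not available in any case, although both scales have a baseline score.

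Two things are at stake for those aims. The first is precision: a week-6 score carries stable differences between patients that the baseline score would partly remove, and with 20 patients there is little information to spare. The second is interpretation: the only stated use of baseline alongside follow-up for these scales is the within-arm Wilcoxon test. If that test is significant in one arm and not in the other, it is easy to report this as a treatment effect, although no between-arm comparison has been made.

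**Working it through.** **Plan's own figure.** The plan gives no power or precision figure for HADS or ACE-R. Its one calculation, under Sample size, concerns VAS-pain: 5 per group at an effect size of 1.73, 80% power and 5% error. A two-sample t-test reproduces it one-sided (power 0.802 at 5 per group); two-sided it would need 7. That does not bear on this point.

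**Inputs from the document.** 10 patients per arm and 1:1 allocation; significance at P < 0.05, taken as two-sided; baseline and week-6 scores for both scales.

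**Assumptions, not in the document.** Baseline to week-6 correlation r from 0.3 to 0.9; a true effect of 0.8 SD; normally distributed scores with equal variance at both visits.

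**Step 1: chance imbalance.** The difference between two baseline means has standard error sqrt(1/10 + 1/10) = sqrt(0.2) = 0.447 SD. The chance of an absolute gap above 0.5 SD is 2 × Φ(−0.5/0.447) = 0.264, or 26%.

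**Step 2: precision.** Relative to the raw week-6 comparison, ANCOVA multiplies the standard error by sqrt(1 − r²), ignoring the small loss from estimating the slope. The equivalent sample multiplier is 1/(1 − r²).

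| r | SE factor | Sample multiplier |
|---|---|---|
| 0.3 | 0.954 | 1.1 |
| 0.5 | 0.866 | 1.3 |
| 0.7 | 0.714 | 2.0 |
| 0.8 | 0.600 | 2.8 |
| 0.9 | 0.436 | 5.3 |

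**Step 3: power by simulation (0.8 SD effect, 10 per arm).**

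| r | Raw Mann-Whitney | Unadjusted t-test | ANCOVA | Rank ANCOVA |
|---|---|---|---|---|
| 0.3 | 35% | 40% | 40% | 39% |
| 0.5 | 35% | 40% | 48% | 45% |
| 0.7 | 35% | 40% | 63% | 57% |
| 0.8 | 35% | 40% | 78% | 68% |
| 0.9 | 35% | 40% | 96% | 89% |

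The step from 35% to 40% is the gain from a parametric rather than a rank test. Only what lies beyond 40% in the ANCOVA column comes from using baseline. At r = 0.3 that is almost nothing.

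**Step 4: false positives by simulation (no effect).** Over all randomisations the raw Mann-Whitney test rejects in about 4% of trials at every r. Among trials with a baseline gap above 0.5 SD it rejects in about 6% at r = 0.3, 9% at 0.5, 12% at 0.7, 13–14% at 0.8 and 15% at 0.9. ANCOVA stays at about 5% in those same trials.

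**Step 5: are two visits an obstacle?** No. With two visits the treatment-by-time term is the same test as a t-test on change, whose variance factor is 2(1 − r). That exceeds 1 when r is below 0.5, so a change score can be worse than the raw score: for an assumed 1.0 SD effect at r = 0.3, power is 43% on change, 56% on the week-6 score alone (t-test) and 60% with ANCOVA. This is why ANCOVA is preferred to a change score.

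**The case against.** The strongest reply is that the planned test is sound and the outcomes are minor. Much of that stands.

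- **Validity.** A reader might infer that a raw week-6 comparison is confounded by who happened to be allocated where. The document does not support that. Allocation is randomised 1:1, and the test holds its level at about 4%. The raised error rate in step 4 applies only after a sizeable baseline gap has been seen.
- **Outcome status.** A reader might infer that the trial's main conclusions are at risk. They are not, because neither scale is a named primary or secondary outcome.
- **Wording.** A reader might infer that the plan rules out comparing change between arms. It does not state such a comparison, and raw scores are the natural reading, but a Mann-Whitney test on change is not excluded.
- **Size of the gain.** A reader might infer that most of the information is being thrown away. At r = 0.5 the sample multiplier is only 1.3, and the document gives no value of r. Excluding major depression may narrow the HADS range and lower r. ACE-R is capped at 100, so normal-theory power may flatter ANCOVA.
- **Patient mix.** Education level is recorded, but no distribution is given, so an argument from varied education would be unsupported.
- **Not unique to these scales.** If the ANOVA assumptions fail, the other four outcomes fall back to the same unadjusted test.

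What remains is that two outcomes in the stated aim have collected baselines that their only stated between-arm test at week 6 is not said to use.

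**Conclusion.** The gap is real and modest in consequence. For HADS and ACE-R the plan states no between-arm comparison that takes account of baseline. The cost is lost precision and exposure to chance imbalance, not an invalid test. Its size depends on an unknown correlation: the gain is negligible at r = 0.3, about 8 percentage points of power over an unadjusted t-test at r = 0.5 (48% − 40%), and 23 to 56 points at r = 0.7 to 0.9 (63% − 40% and 96% − 40%), somewhat less with rank ANCOVA. All of these figures assume normal data and a 0.8 SD effect. Only the mood and cognition aims are affected. The change is an improvement at almost no cost, not the repair of an error that would alter the named results.

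**What to change.** Add a sentence to the Statistical analysis section: week-6 HADS and ACE-R are each compared between arms by ANCOVA with the same scale's baseline score as covariate, using rank ANCOVA if residuals are clearly non-normal, and the adjusted difference is reported with its 95% CI. State that the within-arm Wilcoxon tests are descriptive and are not read as evidence of a treatment effect.

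The cost is one degree of freedom per model (17 residual instead of 18 with 20 patients) and no new data, since both baselines are collected. The document is written in the past tense and already describes 20 enrolled patients. If the data have been analysed, present this as an added analysis and label it so.
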